## E. Specific methods and techniques used throughout the study

1. After screening, informed consent, and enrollment into the study, subjects will be assessed for the following at the CTSU:

**Blood draw** (approximately 8 tubes of blood): complete blood count, complete metabolic panel, lipid panel, inflammatory panel, fasting glucose, 1 hour and 2 hour glucose (oral glucose tolerance test), insulin, glycosylated hemoglobin (HbA1c), serum protein electrophoresis (SPEP), vitamin B12, point of care glucose finger stick (pre- and post-OGTT), heat shock protein (HSP) 72 and 90 **Urine Analysis**: pregnancy test, if applicable

2. Study Procedures: All study visits will be completed at the University of Kansas Clinical and Translational Science Unit (CTSU) by study personnel and CTSU staff. Prior to the first visit, the inclusion and exclusion criteria will be reviewed with a phone screen (included in appendix).

**Visit 1 (pre-intervention evaluation):** During the pre-intervention evaluation (approx. 3.5 hours), inclusion and exclusion criteria will be confirmed via medical history, medication review, and the above listed laboratory tests. Vitals, demographic

information, social and lifestyle information, and questionnaires on lifestyle will also be collected.

Medical History: prediabetes diagnosis and duration, neuropathy diagnosis and duration, family history of diabetes or neuromuscular disorders, general medical history

Medication Review

Vitals: heart rate, blood pressure, height, weight, waist circumference, body mass index (BMI)

Demographic Information: date of birth, sex, race, ethnicity, recruitment source, education level

Social/Lifestyle: marital status, employment status, smoking history

Questionnaires: PROMIS Emotional Distress and Depression, PROMIS Sleep Disturbance (included in appendix).

Following an overnight fast, participants will have blood drawn (6 teaspoons) for analysis at Quest Diagnostics. After initial fasting blood samples (listed above), patients will drink a sweet and concentrated solution of glucose (Azer Scientific Glucola, 75 g) within 5 minutes. After this, patients will wait for 1 hour and blood will be redrawn to test glucose and insulin levels (2 teaspoons). A final blood draw for glucose and insulin will occur after another hour (2 teaspoons). Patients will complete a point of care glucose finger stick to ensure blood glucose is within a safe range before start and after completion of OGTT for safety.

Visit 2 (pre-intervention evaluation): Once inclusion and exclusion criteria are confirmed by laboratory results, the presence and type of neuropathy will be confirmed with a clinical examination and nerve function testing (Drs. [name] or [name], approx. 1.5 hours).

Neuropathy and Pain Assessment: medical evaluation by Drs. [name] and [name], Utah Early Neuropathy Scale (UENS), Quantitative Sensory Testing (QST). Questionnaires: Brief Pain Inventory (BPI), PROMIS Physical Function short form. Skin Biopsy: Patients will undergo a punch skin biopsy from the proximal thigh. Total dermal and epidermal innervation will be quantified from skin biopsies. The punch skin biopsy will be performed using a 3 mm disposable circular punch (Miltex, York, PA) after injection of 2% lidocaine under a sterile technique. No suture will be used. The skin will be placed in freshly prepared Zamboni's fixative for one hour. The tissue will be sectioned at 50 µm and processed for immunohistochemistry using rabbit anti-PGP9.5 primary antibody (1:3000; Chemicon, Temecula, CA). Sections will be coded in order to carry out the analysis in a blinded fashion and quantified. The biopsy will be used for quantification of GLO1 enzymatic activity.

Visits 3-14 (heat therapy intervention x 12 treatments): After the skin biopsy has appropriate time to heal (approximately 7-14 days), the subjects will undergo 30-minute heat treatments in 40°C water, three times weekly, for 4 weeks (approx. 1 hour each).

[figure not shown]
Subjects will be immersed up to the shoulder in a 40°C hot tub until rectal temperature  $(T_{re})$  increases by 1°C (~20 minutes). Subjects will then remain in the water bath submerged to waist level to maintain Tre between 38.5 and 39.0°C for another 30 minutes (approx. total time submerged ~50 minutes). Following hot water immersion, subjects will be monitored for another 10 min, or until Tre falls below 38.5°C. Core temperature will be monitored using either 1) a rectal probe with sterile disposable sheaths or 2) a sterile disposable rectal thermistor probe (401 A/C, Advanced Industrial Systems, Inc., Harrods Creek, KY) to be inserted  $\sim 1$  inch past the anal sphincter

(inserted by participant). Heart rate and blood pressure will be monitored throughout the treatment. Subjects will be continually monitored and removed from the hot bath if  $T_{re}$  exceeds 39.5°C.

**Visit 15 (post-intervention evaluation)**: After completion of heat therapy intervention, subject will return to assess any change in fasting laboratory tests, oral glucose tolerance test, and questionnaires as listed in Visit 1 (approx. 2.5 hours). In addition to the two questionnaires completed at Visit 1, subject will also complete a Patient Global Impression of Change (PGIC) survey (included in appendix). A single question asks patients "After my treatment, my pain is:" with a 7-point scale ranging from -3 (very much worse) to 0 (no different) to +3 (very much improved). This measure will be a secondary determinant of analgesic response to treatment and will only be administered at the completion of heat therapy intervention

**Visit 16 (post-intervention evaluation)**: Subject will return for a final visit to assess any change in the presence or type of neuropathy by completing the same clinical examination and nerve function testing as in Visit 2 (Drs. [name] or [name], approx. 1.5 hours).

- 3. All procedures will be performed solely for research purposes. None should be considered standard of care or billed to insurance.
- 4. Blood will be processed at the CTSU and sent to Quest Diagnostics for resulting. Subjects will have the option to save leftover samples for future deidentified research. Otherwise, any leftover samples will be destroyed. Skin biopsy samples will be housed at the University of Kansas Medical Center in a secure laboratory for processing. Only the study team will have access to any samples. All samples will be marked only with subject ID and date.
- 5. Timeline:

Subjects are expected to complete the study in approximately 11-13 weeks.

#### F. Risk/benefit assessment:

1. Physical risk: Participants will be asked to fast overnight for the blood draw. The study visits will be scheduled in the morning when possible, and subjects will be provided with a snack immediately following testing. Risks of blood draws include temporary discomfort from the needle being inserted into the skin, bruising, swelling, fainting, or in rare cases, infection or blood clot at the injection site.

During the oral glucose tolerance test, there is a very small risk of developing symptoms of low blood sugar, which include rapid heartbeat, sweating, and headache. Nausea and vomiting are also rare, but known, risks of the oral glucose tolerance test. Patients will complete a point of care glucose finger stick to ensure blood glucose is within a safe range before leaving the CTSU. Study personnel will be trained by the investigators to be sensitive to participant discomfort and concerns. Participants will be instructed that they can stop any QST procedure anytime that the pain or unpleasantness of the task becomes unbearable. There have been no significant adverse events associated with any of these procedures in the experience of its use at the Chronic Pain and Fatigue Research Center at the University of Michigan. Specifically, MAST testing may cause some temporary physical discomfort on the thumbnail. The MAST System incorporates a series of redundant mechanical, electrical, and software safety features to prevent patient injury in the event of user error or device failure, including a safety pin that the subject can turn to immediately remove the pressure actuator from his or her thumb. The test is terminated at or before 10 kg/cm2 of pressure which is a commonly used maximum pressure level in human sensory testing and does not result in physical injury. Participants will always have personal control over the stimulus and can stop it at any time or express instructions to stop the stimuli. They can also withdraw their thumb from the device. However, these instruments may cause minor physical discomfort in the areas of testing that is expected to resolve within minutes of test completion.

The 3mm skin biopsy procedure is not painful. However, when the Lidocaine is injected, there may be a brief pinprick pain followed by a few seconds of burning form the anesthesia. A small percentage of patients can have an allergic reaction to the Lidocaine. If an allergic reaction to the Lidocaine occurs, it will be treated immediately with medicines in the clinic. Following the biopsy there will probably be some soreness. There is a risk that the biopsy site will bleed or become infected. The risk for infection is low at the biopsy site. The biopsy will leave a small scar that will fade in intensity over time. There are some risks associated with heat exposure, including: fatigue, light-headedness, muscle cramps, dehydration, and neurological detriments (i.e. heat stroke). However, these symptoms do not typically occur until core temperature rises above 40°C. Core temperature (rectal thermistor) will be continuously monitored and recorded. Subjects will be removed from the hot bath immediately if either core temperature reaches 39.5°C or the subjects experience any symptoms of heat-related illness. All symptoms subside upon lowering core temperature. Ice packs will be on hand if rapid cooling is necessary (see Rapid Cooling SOP). Heart rate will also be continuously monitored and recorded throughout heating. If HR increases > 60 beats/min above resting or increases > 20beat/min with a 5 min time period, subjects will be moved to a seated position if they were previously fully submerged or removed from the hot tub if they were already sitting up. Additionally, heat exposure may have detrimental effect on a developing fetus in females. Thus, subjects who are pregnant or trying to conceive will be excluded from the study. This will be confirmed with a pregnancy test.

- 2. Psychological risk: Some questions related to medical history, weight, or pain status may result in feelings of discomfort or embarrassment. Participants may decline to answer any questions.
- 3. Social risk: N/A
- 4. Economic risk: N/A

- 5. Potential benefit of participating in the study
  - a. Potential benefits for individuals including learning new information based on laboratory testing and medical examination, at no cost to the subject. This information may be of use to the participant and their physician by providing updated information on important parameters of prediabetes and/or neuropathy. Subjects will have the opportunity to receive heat therapy, which may offer multiple health benefits related to the cardiovascular system and metabolic health. Physiological benefits to the cardiovascular system in healthy subjects has been documented and those studies were performed by [name], from the University of Oregon. In addition, quality of life improvements have commonly been reported by patients undergoing chronic heat exposure (e.g. hot tub, sauna, etc.).
  - b. The information gained in this research study will be useful in developing novel treatments of peripheral neuropathy in the future related to prediabetes patients.
  - c. The proposed research will be helpful to develop fundamental knowledge about treatment approaches that will help reduce the burdens of disease and disability. This knowledge should offset the very minor risk to participation by individual subjects, given the protections that are in place and the low likelihood of a serious adverse event in this study.

# H. Collaboration (with another institution, if applicable): $\ensuremath{\mathsf{N/A}}$

# I. Single IRB Review for a Multi-site study (if applicable): N/A

- 1. For which sites will KUMC serve as the IRB of record? N/A
- 2. Indicate which study activities will occur at each site. If all study procedures will be identical across study sites, state this. N/A
- 3. Describe how you will assess the capacity of each site to perform the research (e.g., expertise, staffing, space, equipment, etc.) If applicable, include site evaluation tools in your IRB submission. N/A
- 4. Describe how the lead investigators will ensure that all participating sites use the IRBapproved version of the protocol, consent, recruitment materials and other study documents. N/A
- Describe how the lead investigators will communicate with and disseminate new information to other sites (e.g., training meetings, regularly-scheduled conference calls, notifications, etc.) N/A
- 6. Describe how the lead investigator will assess protocol compliance, unanticipated problems and adverse events at other sites. N/A
- 7. Name the member of the KUMC study team who will be the point of contact to coordinate oversight and communication with the sites. N/A

## J. Community-Based Participatory Research (if applicable)

- 1. Participants and the nature of their involvement: N/A
- 2. Cultural issues: N/A
- 3. Origin of the research question: N/A
- 4. Risks and Benefits: N/A
- 5. Study Description and Process: N/A
- 6. Return of results: N/A
- 7. Sustainability: N/A

# L. Assessment of Subject Safety and Development of a Data and Safety Monitoring Plan

- 1. Elements of the plan include:
  - a. Persons/groups who will review the data (study team; independent safety monitor, data monitoring committee or formal DSMB): The PI or Co-Is will monitor AEs monthly, grade them, and indicate if the AE is related to the study procedure (definite, probably, possible, unlikely, not related). For each AE, the PI will determine if the study procedure should be continued. Patients will be instructed to call the PI's office (or on-call resident/coordinator if at night or on the weekend) to report events that occur between study visits. All SAEs will be reported to the HSC and Clinical Research Center (if applicable) and FDA guidelines, as soon as possible, but no later than five working days.
  - b. Data/events that will be reviewed: Any serious adverse events (SAE) will be reviewed as soon as possible and reported to the IRB if applicable.
  - c. Frequency of review: Data safety will only be monitored if necessary (unusually high frequency of adverse events (AE) or at any SAE).
  - d. Types of analyses to be performed: N/A
  - e. Safety-related triggers that would cause the PI to stop or alter the study: N/A -Study activities are considered low risk and any adverse symptoms will be treatment promptly, including temporary removal from heat treatment. Will assess if further safety-related triggers need to be identified as needed.
- 2. Nursing staff will continually monitor participants for adverse events. Any adverse event will be immediately reported to the PI and study coordinator per KUMC Human Subject Committee reporting policies. AEs will be classified as follows: related to study procedure as determined by the PI or unrelated to study procedure (related instead to underlying disease, pre-existing conditions, or other factors), anticipated (included in consent form) or unanticipated (not included in consent form), serious (SAE, Grade 4 using CTCAE v3.0) or not serious (AE, Grade 1, 2 or 3 using CTCAE v3.0)
- AEs that are not related to study procedures or are otherwise considered anticipated, low-risk events (ie: bruising or bleeding at injection site) will be monitored and recorded, but not necessarily reported to the medical monitor or the HSC unless frequency of event is considered unanticipated.

Any AEs that are related to study procedure, are unanticipated, and are considered serious will be reported to the medical monitor and to HSC. A report that summarizes the frequency of all AEs will be provided to the medical monitor as needed. If a patient experiences a serious adverse event, they will be discontinued from the study.

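### No rule holds new heat-therapy starts after a serious heat event, and the reporting rule may leave a foreseen heat stroke with no mandatory route to the medical monitor

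*Combined protocol and SAP*

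**What the plan says.** All references are to the combined protocol and SAP.

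**Study-level triggers.** II.L.1.e answers "N/A -Study activities are considered low risk and any adverse symptoms will be treatment promptly, including temporary removal from heat treatment". The next sentence adds "Will assess if further safety-related triggers need to be identified as needed", with no criterion.

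**Risk and aim.** II.F.1 names heat stroke among the risks of heat exposure. I.A includes safety in what the study sets out to confirm.

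**Existing safeguards.**
- Session level (II.F.1): removal from the bath at a core temperature of 39.5°C or on symptoms of heat illness, and heart-rate limits that lead to a change of position or removal.
- Reporting to the PI (II.L.2): "Any adverse event will be immediately reported to the PI and study coordinator per KUMC Human Subject Committee reporting policies".
- PI decision (II.L.1.a): "For each AE, the PI will determine if the study procedure should be continued".
- SAE handling: review as soon as possible (II.L.1.b), data-safety monitoring at any SAE or at an unusually high AE frequency (II.L.1.c), and all SAEs to the HSC within five working days (II.L.1.a).
- Affected participant (end of II.L): "If a patient experiences a serious adverse event, they will be discontinued from the study".

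**Route to the medical monitor.** The closing paragraph of II.L states: "Any AEs that are related to study procedure, are unanticipated, and are considered serious will be reported to the medical monitor and to HSC". II.L.2 defines an anticipated event as one in the consent form, and a serious one as CTCAE v3.0 Grade 4. It lets the study team leave some events unreported to the monitor: "AEs that are not related to study procedures or are otherwise considered anticipated, low-risk events", unless their frequency is unanticipated. The monitor otherwise receives an AE frequency summary as needed.

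**The concern.** The protocol foresees a serious harm, and its safety plan then declines to say what would follow from it for the study. After a serious heat event the PI knows at once and must make a decision. Nothing says that the next participant waits for that decision, or that it concerns the study as well as the affected person.

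The reporting rule adds a separate problem. Because anticipated means disclosed in the consent form, disclosing a serious risk takes the event out of the rule that would send it to the medical monitor. At stake are participants who have not yet been heated, and whether someone other than the PI advises before heating goes on.

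**Working it through.** The plan states no stopping boundary, event rate or power figure to reproduce. The check is a trace of the rules, followed by simple arithmetic for scale.

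**1. Trace of a procedure-related Grade 4 heat stroke, assuming the consent form lists it**

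| Question | Result | Source |
|---|---|---|
| Session ended? | Yes | II.F.1 |
| PI told at once? | Yes | II.L.2 |
| PI decides on continuing? | Yes, but participant or study is not stated | II.L.1.a |
| Reviewed as an SAE? | Yes | II.L.1.b, II.L.1.c |
| Sent to the HSC? | Yes, within five working days | II.L.1.a |
| Participant discontinued? | Yes | end of II.L |
| New starts held? | No sentence says so | II.L.1.e answers N/A |
| Must go to the monitor? | No: related yes, serious yes, unanticipated no | end of II.L |
| Covered by the exemption? | No: it is related and not low-risk | II.L.2 |

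The event falls between the last two rules: not required to go to the monitor, and not exempted either. If the consent form does not list heat stroke, the event is unanticipated, all three conditions are met, and it goes to the monitor. The result on new starts is the same either way.

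**2. The same trace at Grade 3.** The classification is "serious (SAE, Grade 4 using CTCAE v3.0) or not serious (AE, Grade 1, 2 or 3 using CTCAE v3.0", so a Grade 3 heat event is not serious. It gets the immediate report and the PI's decision, but no SAE review, no SAE report and no discontinuation rule. The closing paragraph does not send it to the monitor whatever the consent form says.

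**3. How often a first-event hold would fire.** Input from the plan: n = 20 treated (II.C.3). Assumption: a per-participant probability p of a procedure-related heat illness of Grade 3 or higher. The documents give none, so a range is shown. Formula: P(at least one) = 1 − (1 − p)^20.
- p = 1%: 1 − 0.99^20 = 0.182
- p = 2%: 1 − 0.98^20 = 0.332
- p = 5%: 1 − 0.95^20 = 0.642
- p = 10%: 1 − 0.90^20 = 0.878

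A second-event hold would fire with probability 0.017, 0.060, 0.264 and 0.608, so at low rates it would seldom act.

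**4. How many would still be unheated.** Further assumption: participants are treated one after another. With q = 1 − p, the mean position of the first event, given that one occurs, is 1/p − 20q^20/(1 − q^20).
- p = 1%: 100 − 20 × 0.8179/0.1821 = 10.17, leaving 20 − 10.17 = 9.83
- p = 2%: 50 − 20 × 0.6676/0.3324 = 9.83, leaving 10.17

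If two later participants have already started, these fall to 7.97 and 8.29.

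**5. What that means in events.** Expected further events among the unheated, given a first event, are 9.83 × 0.01 = 0.10 and 10.17 × 0.02 = 0.20. Multiplied by the chance of a first event, they are 0.10 × 0.182 = 0.02 and 0.20 × 0.332 = 0.07. These are ceilings on what a hold could avert: the PI might have paused anyway, and the review might let heating resume.

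**The case against.** The strongest defence is that oversight is already close. Every AE reaches the PI at once, the PI decides on each one whatever its grade, an SAE prompts a data-safety review, and the HSC, which is outside the study team, hears of every SAE. Heating is monitored continuously with a 39.5°C limit, and II.F.1 says heat symptoms are not typical until core temperature passes 40°C. In a single-arm pilot of 20, case-by-case judgement may be thought enough. All of this stands, and it keeps the point small. It does not supply a hold on new starts.

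A reader might draw four stronger conclusions that the documents do not support.
- *The study has no safety stopping or oversight.* It has the safeguards listed above. The PI's decision can also be read as covering the whole study; its scope is simply not stated.
- *The N/A answer is what keeps a heat stroke from the monitor.* It is not. That gap comes from the unanticipated condition in the closing paragraph of II.L.
- *A heat stroke would certainly miss the monitor.* This depends on a consent form that is not available here. The as-needed summary might also bring the event to the monitor, though nothing requires it.
- *The firing probabilities show the harm a hold would prevent.* They show how often it would operate. The ceiling on events averted is far lower at low rates, and the 18% and 33% are also the chance of a pause that may prove unnecessary.

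**Conclusion.** The point holds as two separate gaps, and is worth considering rather than essential. First, no rule makes new starts wait after a serious heat event, although the protocol foresees one; this rests on the text alone. Second, if the consent form lists heat stroke, a related Grade 4 heat stroke has no mandatory route to the medical monitor; this rests on that one assumption. The unstated scope of the PI's decision is an ambiguity that one sentence resolves.

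The numerical stakes are modest and rest on assumed rates and sequential treatment: at 1% to 2% per participant, at most about 0.02 to 0.07 expected events averted over the study. The case for the change is that it settles in advance, at little cost, who waits and who is told.

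**What to change.** 1. **II.L.1.e.** Replace N/A with one trigger: after one procedure-related heat illness of CTCAE Grade 3 or higher, including any heat stroke, no new participant starts heat until the PI and the medical monitor to whom the plan already refers have reviewed the event and recorded a decision to continue, modify or stop. Mild expected symptoms (fatigue, light-headedness, cramps) and single removals at 39.5°C do not count. The paragraph should also say whether fainting and dehydration needing treatment count.
2. **Closing paragraph of II.L.** Delete the unanticipated condition, so that every related serious event goes to the medical monitor and the HSC. Add that any event meeting the II.L.1.e trigger also goes to the monitor. Changing II.L.1.e alone would leave two conflicting reporting rules.
3. **II.L.1.a.** State that the PI's decision covers both the participant and the study.

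The choice of Grade 3 and of a single event is a judgement, and the sponsor may prefer another threshold. The cost is a short amendment and, if the trigger is met, a short review by two existing roles, with no new committee or data. The downside is an occasional unneeded pause in new starts: 18% or 33% over 20 participants at assumed rates of 1% or 2%, and more often if the true rate is higher.

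### Seriousness is defined by CTCAE grade alone, so a Grade 3 event that leads to hospitalisation is classed as not serious and misses the automatic SAE steps

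*Combined protocol and SAP*

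**What the plan says.** The classification is in II.L.2 and is worded as the rule for all adverse events, not as an example. On seriousness it reads "serious (SAE, Grade 4 using CTCAE v3.0) or not serious (AE, Grade 1, 2 or 3 using CTCAE v3.0"). Relatedness and expectedness are classified separately in the same sentence.

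Several steps in II.L depend on the result:

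- **Reporting (II.L.1.a):** "All SAEs will be reported to the HSC and Clinical Research Center (if applicable) and FDA guidelines, as soon as possible", with an outer limit of five working days.
- **Review (II.L.1.b and II.L.1.c):** "Any serious adverse events (SAE) will be reviewed as soon as possible and reported to the IRB if applicable", and "Data safety will only be monitored if necessary (unusually high frequency of adverse events (AE) or at any SAE").
- **Discontinuation (closing paragraph of II.L):** a participant who has a serious adverse event is taken off the study.

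Other provisions apply whatever the class. Under II.L.2, "Any adverse event will be immediately reported to the PI and study coordinator per KUMC Human Subject Committee reporting policies". Under II.L.1.a the PI or co-investigators monitor and grade events monthly, and "For each AE, the PI will determine if the study procedure should be continued".

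**The concern.** Severity and seriousness are different properties. A grade says how intense an event was; seriousness says what it led to. Here the first stands in for the second, so an event with a serious consequence can be filed as not serious because of its grade.

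The SAE label matters more than usual in this plan because little else is defined. The other trigger for data-safety review in II.L.1.c, an unusually high frequency of events, has no number attached, and a single admission would not plainly meet it. II.L.1.e lists "Safety-related triggers that would cause the PI to stop or alter the study: N/A", followed by a statement that symptoms will be treated promptly, with temporary removal from heat if needed, and that further triggers will be considered as needed. Any SAE is thus the only defined trigger for data-safety review.

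Participants are aged 45 to 75 (II.D) and have core temperature held at 38.5 to 39.0°C in each of 12 sessions (II.E, Visits 3-14). II.F.1 names dehydration and heat stroke among the risks of heat exposure, and either could lead to admission. Section I.A.2 gives safety in patients as one thing to be confirmed, and II.C says the pilot is to inform a larger study. An SAE count based on grade alone could understate what that study needs to know.

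**Working it through.** The plan gives no figure to reproduce on this point. The check is to put cases through the written rule and see which steps follow.

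**Inputs.** Classification: II.L.2. Steps that depend on it: II.L.1.a, II.L.1.b, II.L.1.c and the closing paragraph of II.L. I found no outcome criterion for seriousness elsewhere in the protocol text. The text between II.F and II.H, and between II.J and II.L, was not available to check.

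| Event | Class under II.L.2 | HSC report within five working days | SAE review | Discontinuation |
|---|---|---|---|---|
| Grade 4, any outcome | Serious | Automatic | Automatic | Automatic |
| Grade 3, hospitalised | Not serious | Not automatic | Not automatic | Not automatic; PI decides |
| Grade 3, not hospitalised | Not serious | Not automatic | Not automatic | Not automatic; PI decides |
| Death, if Grade 5 | None assigned | Not stated | Not stated | Moot |

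The second and third rows are identical: hospitalisation changes nothing under the rule. That result needs nothing outside the document, since the text places Grade 3 in the non-serious class without qualification. The last row needs an assumption. The plan assigns a class only to Grades 1 to 4 and does not say how a death is graded.

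II.L.1.b and II.L.1.c are counted together as one review step. A further report, to the medical monitor and the HSC in the closing paragraph of II.L, requires an event to be related, unanticipated and serious. A Grade 3 admission would fail its third condition. It is not counted separately because it overlaps the HSC report and carries two extra conditions.

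**Cost of an extra withdrawal.** If more events become SAEs and the discontinuation rule stays as it is, a participant could be lost from the pre-post comparison. For the paired t-test in V.A, the 95% confidence interval half-width in units of the SD of the differences is t(0.975, n-1)/√n:

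- n = 20: 2.093/4.472 = 0.468
- n = 19: 2.101/4.359 = 0.482
- Ratio: 0.482/0.468 = 1.03, or about 3% wider at the same SD

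One participant is 1/20 = 5% of the sample. This prices the remedy; it does not measure the defect.

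**The case against.** The strongest reply is that a Grade 3 admission would not go unnoticed. The PI and coordinator are told of every event at once, the PI decides on continuation event by event, and the immediate-notice sentence refers to KUMC policies, as II.L.1.a refers to FDA guidelines. II.F.1 also requires removal from the bath at 39.5°C or at any symptom of heat-related illness, and says such symptoms are not typical until core temperature exceeds 40°C. All of this stands. A reader might infer that nothing at all happens after a Grade 3 admission, and the documents do not support that. What is lost is the automatic character of the steps. The references to FDA guidelines and KUMC policies govern reporting: they might restore that step, but they do not replace an explicit definition in the same section.

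Three other stronger readings should be resisted:

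- **That heat stroke or dehydration here would be graded 3.** The documents do not say what grade either would receive. The gap is in the rule; no particular event is shown to fall into it.
- **That a death would go unreported.** This rests on the Grade 5 convention and on staff following the letter of the classification, which is unlikely.
- **That II.L contradicts itself by relaxing reporting for "AEs that are not related to study procedures or are otherwise considered anticipated, low-risk events" while requiring it for all SAEs.** The relaxation is permissive, and the term AEs can be read there as the Grade 1 to 3 class just defined. It is at most an ambiguity for SAEs judged unrelated.

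The stakes are also limited. This is a single-arm pilot of 20 participants, and the objective in II.A and the outcomes in V name no safety endpoint.

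**Conclusion.** The point holds as a defect in the written rule. Because seriousness is grade alone, a Grade 3 event leading to hospitalisation is expressly not serious, and none of three steps (the five-working-day HSC report, the SAE review, discontinuation) follows automatically. They depend on the PI's judgement and on policies that are not supplied. A death is also unclassified, on the assumption that it would be Grade 5; the main conclusion stands without that assumption.

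The size cannot be put as a number of events because no SAE rate is given. The primary outcomes, fasting glucose and intraepidermal nerve fibre density, are unaffected. The rule gives a wrong answer for a plausible class of event and is cheap to correct, so it should be fixed.

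**What to change.** In II.L.2:

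1. Keep CTCAE grade as a measure of severity only.
2. Define an SAE by outcome: death, life-threatening event, hospitalisation or its prolongation, persistent disability, or another medically important event.
3. State that the reporting in II.L.1.a, with its five-working-day limit, applies to every event so defined.

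The cost is a wording edit and perhaps a few more reports. With the discontinuation rule unchanged, the wider definition could also add a withdrawal, at the loss of precision shown above.

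The sponsor could limit automatic discontinuation to SAEs related to a study procedure and leave unrelated ones to the PI. That would avoid withdrawals for unrelated admissions, but it loosens an existing protection, since someone with a serious event judged unrelated could return to whole-body heating. It is an optional choice and not part of the required change.
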